Basic Assessment of Safety and Minimally invasive stimulation via Injectrode (BASMATI)

Title: **BASMATI** - Basic Assessment of Safety and Minimally invasive stimulation via Injectrode.

Protocol number: NCP-01

Device: Neuronoff Basmati Injectrode

Sponsor: **Neuronoff, Inc.**
[name]

Sponsor Contact: [name]
[contact]
[contact]

Investigator: [name]
[name]
[name]
[contact]

Study Sites: The Ohio Pain Clinic
[name]
[name]
[contact]

Medical Monitor: Kettering Health Network
Kettering Innovation Center
[name], PHD
[contact]

Revision	Revision Date	Sections Revised	Description	Person Issuing Change	DCO#
A	20201012	All	Initial Release	[name]	0041

Confidentiality Statement

This document contains confidential information that is the property of Neuronoff, Inc. and is subject to all of the restrictions on use and disclosure contained in the study contract to which this is appended. Do not copy, disclose, circulate or use for benefit for any third party without written authorization from Neuronoff, Inc.

Protocol Synopsis

Sponsor	Neuronoff, Inc.
Contact Information	[name]
Title of Trial	BASMATI - B asic A sessment of S afety and M inimally i nv A sive s Timulation via I njectrode.
Objective	The objectives of this non-significant risk (NSR) study are to evaluate the safety of the short term placement of the Basmati Injectrode for up to 28 days and the efficacy of conducting electrical current to stimulate subcutaneous nerves on the explant date just prior to explant.
Clinical Hypothesis	The 28 day temporary placement of a Basmati Injectrode does not result in unexpected levels of inflammation or encapsulation.
Investigational Device	A proprietary bio-electronic medical device (Neuronoff Basmati Injectrode Insert) which is capable of transmitting small electrical currents to stimulate sensory nerves.
Study Device description	The Basmati Injectrode is a gold wire coil formed into the shape of a grain of rice of 10mm length by 4mm width by 2 mm height. This gold material is of 99.99% purity and used in predicate medical devices as lead or electrode material in neuromodulation applications.
Comparative Data	Histopathological report describing findings in rodents with sub-chronic and chronic placement of the Injectrode (REC-020).
Study Design and Scope	The proposed study is a prospective, single-center, single-arm, non-randomized design. Up to 10 study subjects will be provided with the placement of an Injectrode insert. The maximal placement duration will be 28 days. Subjects selected to participate in the trial are healthy without any preexisting condition indicated to be treated. Each subject will be followed during the trial period of approximately 50 days, including the time for screening and post-explant follow-up. The study will end when the last subject has completed the trial period and exited. After exit from the clinical study, subjects will continue to be followed by their physician per standard of care. All device and procedure-related adverse events (AEs) and unanticipated problems (UPs) will be collected and reported per the study protocol.
Planned Enrollment	We plan to enroll and screen up to 20 study participants, of which up to 10 participants will be provided with a Basmati Injectrode Insert for the trial.
Primary Safety Objective	Primary measures of device safety will include verification of the absence of unexpected inflammation and minimization of excessive encapsulation around the Injectrode as verified by cell staining and pathohistological analysis.
Secondary Effectiveness Objective	Secondary measures of device effectiveness will include impedance and stimulation threshold measurements for subcutaneous nervous tissue.

STUDY FLOWCHART

[figure not shown]

Table of Contents

	Page
PROTOCOL TITLE	I
PROTOCOL SYNOPSIS	II
FLOWCHART	III
TABLE OF CONTENTS	IV
LIST of ABBREVIATIONS AND DEFINITIONS	VI
INTRODUCTION	1
BACKGROUND AND RATIONALE	1
CURRENT TREATMENT APPROACHES AND SHORTCOMINGS THEREOF	1
CLINICAL NEED FOR A “LAST MILE CONNECTION” TO CONNECT TO A NERVE	2
RATIONALE FOR THE NON-SIGNIFICANT RISK CLASSIFICATION OF THIS STUDY	4
COMPARISON TO EARLIER STUDIES	5
STUDY PARTICIPANT SAFETY	6
PRE-CLINICAL DATA / SUMMARY OF PREVIOUS STUDIES	6
OBJECTIVES	7
PRIMARY OUTCOME MEASURES: SAFETY	8
SECONDARY OUTCOME MEASURES: INTERFACING EFFICACY	8
DEVICE	9
NEURONOFF BASMATI INJECTRODE INSERT	9
REGULATORY CLASSIFICATION	11
STUDY DESIGN	12
SCHEDULE OF EVENTS (SOE)	13
OUTCOMES	14
PRIMARY SAFETY OUTCOME MEASURES	14
SECONDARY SAFETY OUTCOME MEASURES	14
MINIMIZATION OF BIAS	15
INVESTIGATORS	16
INVESTIGATOR SELECTION AND RESPONSIBILITIES	16
STUDY POPULATION	17
INCLUSION CRITERIA	17
EXCLUSION CRITERIA	17
SAMPLE SIZE	18
METHODS AND PROCEDURE	19
DATA COLLECTION REQUIREMENTS	19

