4.0 STUDY DESIGN

The proposed study is a prospective, single-center, single-arm, non-randomized design. The study will screen up to 20 subjects for study eligibility and potential enrollment. Up to 10 study participants will be provided with the placement of a Basmati Injectrode insert. The maximal placement duration will be 28 days. Subjects selected to participate in the trial will be solely healthy volunteers without any preexisting condition indicated for treatment. Each subject will be followed during the trial period of approximately 45+/-2 days.

The study will end when the last subject has completed the trial period and exited. The expected enrollment period for this study is approximately 2 months. After exit from the clinical study, subjects will continue to be followed by their physician per standard of care. All device and procedure-related AEs and UPs will be collected and reported per the study protocol.

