9.1.9 POST-EXPLANT VISIT & STUDY EXIT (IN-PERSON, day 42 +/- 2)

A Study Exit CRF must be completed for any subject who signed an informed consent form, as they are considered enrolled in the study. Data to be collected at this visit include study exit date and reason for study exit, device or procedure related AEs, technical observations/device deficiencies and surgical interventions.

Some scenarios may lead to study exit and require completion of a Study Exit CRF: These include subject ineligibility for the implant in the opinion of the study physician, failure to meet inclusion criteria, meeting exclusion criteria, removal of the SCS lead without re-implantation, attempted implant without SCS implantation, voluntary withdrawal by the subject, subject withdrawal by the investigator, failure to maintain adequate study compliance and/or subject death.

Assessments and Data Collection	Screening and Enrollment	Call for patch removal	Injectrode Placement	Follow-up visits	Efficacy and Explant visit	Post study follow-up
Day (relative vs. Placement)	-5 to -4	-2	0	7 ± 2 14 ± 2	28 (-2 to 0)	42 ± 2
● Eligibility confirmation	✓					
● Medical history	✓					
● Physical exam	✓					
● Informed consent	✓					
● Record demographics	✓					
● Verification of absence of allergy to gold & pregnancy test	✓					
● Confirmation of study eligibility	✓					
● Removal of skin patch		✓				
● Read skin test patch results			✓			
● Basmati placement procedure			✓			
● Ultrasound & Fluoroscopy image capture			✓		✓ (pre & post)	(✓)
● Capture of images of surgical site	✓		✓ (post)	✓ (✓)	✓	✓ (✓)
● Remove skin suture(s) if placed during surgery						
● Measure impedance needle to needle connection					✓	
● Measure stimulation thresholds					✓	
● Removal procedure					✓	
● Study participant exit						✓

Table 6: Focus on Post study follow-up

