10.0 ADVERSE EVENT REPORTING

During the study, the investigator will determine whether any adverse events (AE's) have occurred. For the purpose of this protocol, an adverse event is any undesirable clinical occurrence in a subject that can be attributed to the device or incision closure procedure.

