10.1 ADVERSE EVENTS

In this study, study participants should be encouraged to report AE's spontaneously or in response to general, non-directed questioning (e.g., "How has your health been since the last visit?") per Neuronoff SOP-38. Any time during the study, the study participant may volunteer information about any event that resembles an AE. If it is determined that an AE has occurred, the investigator should obtain all the information required to complete the AE Form of the CRF.

The following categories of adverse event severity are to be used:

Mild	Awareness of a sign or symptom that does not interfere with the study participant's usual activity or is transient, resolved without treatment and with no sequelae
Moderate	Interferes with the study participant's usual activity
Severe	Any fatal or immediately life-threatening clinical experience that requires a subject to be hospitalized, or hospitalization is unduly prolonged because of potential disability or danger to life or because an intervention has been necessitated. This includes events that cause fetal distress, fetal death, congenital abnormality or malignancy or any permanently disabling event.

Table 7: Categories of adverse event severity

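### Attribution to the device or procedure is the entry condition for AE data, so the AE listing of this uncontrolled first-in-human study may be biased downward

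*Protocol*

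**What the plan says.** Five places in the protocol bear on which events become AE data.

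- **Synopsis, Study Design and Scope:** "All device and procedure-related adverse events (AEs) and unanticipated problems (UPs) will be collected and reported per the study protocol".
- **4.0 Study Design:** the same sentence in short form, "All device and procedure-related AEs and UPs will be collected and reported per the study protocol".
- **10.0 Adverse Event Reporting:** "the investigator will determine whether any adverse events (AE's) have occurred". The definition to be applied in doing so reads: "an adverse event is any undesirable clinical occurrence in a subject that can be attributed to the device or incision closure procedure". Attribution is thus part of the term itself.
- **Section 10.1, on recording:** participants are encouraged to "report AE's spontaneously or in response to general, non-directed questioning". Then: "If it is determined that an AE has occurred, the investigator should obtain all the information required to complete the AE Form of the CRF".
- **9.1.9 Post-Explant Visit & Study Exit:** the exit data include "device or procedure related AEs".

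No section asks for all untoward events to be recorded with relatedness rated separately, and none describes an independent review of causality.

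**The concern.** Usual practice is to record the event first and judge its cause second. Here the order is reversed: the judgement of cause decides whether there is an AE at all. The person judging knows that every participant carries the device, works at the only site, and has no earlier human experience with the device to draw on. Under 9.1.7 the day 7 and day 14 contacts may be telephone calls, so some of these judgements may be made without an examination.

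Without a control arm, the link between a device and a non-local symptom is rarely visible in one person. It tends to show when the same symptom turns up in several participants. Filtering case by case can remove the material from which that pattern would be seen. The data are also meant to support a second study with deeper placement (1.3 and 1.4), so an AE listing that is too short would carry forward. An analysis plan could not repair this, because it can only work with what was collected.

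**Working it through.** **Step 1: trace an event through the text.** Take a participant who mentions a non-painful, non-local symptom at day 14.

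1. The general health question in 10.1 would elicit it, since that question is not limited to the device.
2. The investigator then decides whether it is an AE (10.0). The test is attribution to the device or to incision closure.
3. If the answer is no, 10.1 does not call for the AE Form.
4. At exit, 9.1.9 again asks for related AEs.
5. In Table 9 (section 10.3) the reporting lines are death, unanticipated adverse device effects and other adverse device effects. A non-fatal event judged unrelated, even a serious one, has no line there.

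**Step 2: find the operative text.** The Synopsis and 4.0 say that related events will be collected; they do not say that others are excluded. The 10.1 trigger is not a causality filter by itself, because any AE form follows a decision that an AE occurred. Both become a filter through the definition in 10.0. That definition is also narrower than the Synopsis: it names the device and incision closure, but not placement, electrical testing or explant. The abbreviation list keeps AE apart from ADE and SAE apart from SADE; section 10.0 in effect reduces AE to ADE.

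**Step 3: list what is kept whatever the attribution.**

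| Source | Where | What it can preserve |
|---|---|---|
| CRF record of pain or discomfort | 5.0 | painful events |
| Site photographs, ultrasound, fluoroscopy | 5.0 | visible or local changes |
| Independent histopathology | 9.1.8 | tissue response at the implant |
| Death report | Table 9 | deaths |
| Source documents, open to monitors and retained | 13.3, 13.6 | whatever was charted, unstructured |
| Unanticipated problems | Synopsis, 4.0, 5.0 | unclear, as the term is not defined |

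What remains without an assured place is the non-painful or systemic event that was judged unrelated.

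**Step 4: size.** The protocol states no AE rate, power or interval, so there is no figure to reproduce. Two calculations show what is sensitive.

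*(a) How far one event moves the result at n = 10 (8.3).* Exact two-sided 95% limits:
- 0 of 10: upper limit 1 − 0.025^(1/10) = 30.8%.
- 1 of 10: 0.3% to 44.5%.

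One dismissed event is thus the difference between these two statements.

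*(b) Hypothetical only.* Let p be the true proportion of participants with a given device reaction and d the share of those reactions wrongly judged unrelated. Neither has a source in the protocol. With independent judgements, P(none listed) = (1 − p(1 − d))^10.

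| p | d = 0 | d = 25% | d = 50% |
|---|---|---|---|
| 10% | 34.9% | 45.9% | 59.9% |
| 20% | 10.7% | 19.7% | 34.9% |
| 30% | 2.8% | 7.8% | 19.7% |

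Example: p = 20%, d = 50% gives (1 − 0.10)^10 = 34.9%.

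One investigator makes all the judgements, so independence is doubtful. If that person dismissed a symptom type either always or never, P(none listed) = d + (1 − d)(1 − p)^10, which for p = 20%, d = 50% is 0.5 + 0.5 × 0.107 = 55.4%. If recurrence led the investigator to reconsider, the figure would fall back towards 10.7%. The direction is clear; the amount is not.

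**The case against.** **The tempting stronger reading.** A reader might infer that a dismissed reaction leaves no trace and cannot be looked at again. The protocol does not support that. The sources in Step 3 carry no attribution condition or, for source documents, can be inspected later. This part of the objection stands, and the point is limited accordingly.

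**The wording is lenient.** Section 10.0 speaks of what can be attributed, which may be read as possible relatedness, a low threshold. Allergic reaction and implant-site infection are listed as anticipated in 10.2, so the investigator is already alert to a rash or fever. This lowers the likely number of dismissals. It does not change the order: the judgement still precedes the record.

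**The primary outcome is untouched.** The primary safety measure is histopathology (2.1, 5.1), which no attribution filters, and 11.2 says that the study is not powered. This stands. The exposure is confined to the AE listing, which is nevertheless the main record of clinical, as opposed to tissue, safety.

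**Unseen documents.** The AE procedure (SOP-38) and the CRF template are listed but not shown, and may collect more widely. If they do, they conflict with 10.0 and the protocol text still needs changing.

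**Any numerical size is assumed.** This stands in full. The tables illustrate and carry no evidential weight.

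**Conclusion.** The point holds in a limited form. The protocol states a rule, and does not merely leave a detail open, under which attribution by the investigator decides entry to the AE data. The definition in 10.0 is the operative text; the Synopsis, 4.0, 9.1.9 and 10.1 follow it. Section 6.0 names evaluation of study data as a source of bias, but the measures it lists (eligibility screening, demographics, training) do not address attribution.

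The consequence is that non-painful or systemic events judged unrelated have no assured place in the AE data, that the listing may be biased downward, and that attributions cannot be reviewed systematically. The size cannot be derived from the protocol. The conclusion assumes that the unseen procedure and CRF follow the protocol text, and that an undefined category such as unanticipated problems is not used to record all-cause events. It does not extend to the histopathology outcome. This should be changed before enrolment, since events not recorded at the time may be hard to recover.

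**What to change.** 1. **10.0:** define an AE as any untoward clinical occurrence from placement to study exit, regardless of cause. This edit must come first. Changing only the other sections would leave them in contradiction with the definition.
2. **Synopsis, 4.0, 9.1.9, 10.1:** align the collection scope with that definition, and have the AE Form completed for every such event.
3. **AE Form:** rate relatedness to device, placement, electrical testing and explant in a separate field, after the event is entered. Confirm first whether the unseen form already has one.
4. **Reporting:** show the device- and procedure-related subset as now, with the all-event listing beside it.
5. **SOP-38 and the CRF template:** check that both agree with the revised text.

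The cost is small: a text amendment, at most one field, and extra entries for at most 10 participants over about six to seven weeks (exit is day 42 in 9.1.9 and day 48 in Table 1; 42/7 = 6.0 and 48/7 = 6.9). The downside is that a few unrelated events will appear in the listing.

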1.0 INTRODUCTION

1.1 Background and rationale

Neuromodulation, sometimes referred to as Bioelectronic Medicine, is using electrical stimulation or blocking of neural activity to achieve beneficial effects in the human body. These effects can include the reduction of chronic pain, reducing the frequency of overactive bladder, epileptic events, up to a modulation of the metabolic activity of inner organs. In many cases, afferent and efferent nerves of interest for interfacing are located within 5 cm when measured from the surface of the skin. Unfortunately, extracorporeal means of modulating neural activity in these nerves cannot be achieved reliably by widely available technologies such as Transcutaneous Electrical Nerve Stimulation (TENS) as the electric field applied on the outside of the skin only penetrates a few millimeters into the body before current densities have dissipated enough to limit the ability to reliably activate or deactivate neural tissue.

In order to electrically interface with these nerves, the clinical standard today is to place an implantable pulse form generator (IPG) into the patient, followed by one or more electrodes connecting the IPG to the nerve of interest by means of an open cut-down procedure. This often requires general anesthesia, a surgeon to place the devices, and commonly results in significant scarring visible post surgery as well as a large burden on the payer in the healthcare system for the cost of the extensive procedure.

1.2 Current treatment approaches and shortcomings thereof

Today, individuals suffering from chronic intractable pain of the trunk and/or limbs are typically treated on a continuum with less invasive therapies prescribed first. Established, non-surgical treatment options include, but are not limited to, oral medications including opioid-based drugs, physical therapy, TENS, acupuncture, nerve blocks, radiofrequency ablation and other options based on clinical judgment. The surgical treatment options for these study participants include surgery of the spine, sympathectomy, intrathecal drug pumps, and spinal cord stimulation (SCS) systems¹.

Neuromodulation offers many treatment solutions to pathologies such as Parkinson's Disease, peripheral nerve pain, overactive bladder (OAB) and neuralgia among others. Current solutions are divided between invasive, minimally invasive and non-invasive treatments and each come with their own set of challenges and benefits. Invasive treatments generally require surgery under anesthesia to place signal generators, leads and electrodes, often resulting in visible scars and are the most expensive treatment option. Non-invasive treatments typically have the least efficacy, reliability problems, limited applicability to a few locations and no ability to block nerves. Only few invasive treatments exist and those generally require a bulky external signal generator, and often don't provide the option to place an electrode as a cuff around a nerve, a necessary requirement for optimal mechanical and electrical interfacing for the long term. For many potential applications that could be treated with

¹ American Chronic Pain Association Resource Guide to Chronic Pain Medication and Treatment, 2014 Edition.

neuromodulation technology, nerves of interest are located deeper than 5 mm when measured from the surface of the skin. This limitation of non-invasive TENS technology to nerves only very close to the skin is greatly holding back the development of novel treatments using neuromodulation.

There is a need for a technology that conducts an externally generated signal to a nerve of interest to locations from just beneath the skin to a target nerve at a depth of up to 5cm.

1.3 Clinical need for a “last mile connection” to connect to a nerve

The future of neuromodulation is expected to become more patient centric and will focus on various unserved needs patients have today. One of these needs is to be free from the need to undergo revision surgeries every 3 to 7 years to replace an exhausted battery by explanting an old neuromodulation device and reimplanting a new one in its place. In addition, a second need is to minimize the prevalence and size of scars caused by the surgery to place first an electrode on a nerve target and second the scar caused by the placement of the signal generator.

Neuronoff, Inc. set out to provide a solution to both of these needs by electrically connecting the nerve with an insert that can be delivered via needle puncture to minimize scarring². The insert functions as an electrical conduit (coupler), transferring current applied to the skin (e.g. via TENS) via a very low impedance down to the nerve of interest (figure 1). In essence, this conduit provides the last mile connection for electrical signals from the skin to the target nerve.

[figure not shown]

Figure 1: Comparison between the **Target Product** (A-C) and the **BASMATI Injectrode** insert (D). While electrical energy applied by a TENS unit does only reach approximately 3 to 5 mm deep (A), a low impedance conduit (B) can conduct electrical energy to a location more distant inside the body to activate a nerve (C). The BASMATI insert is manufactured following similar procedures and from the same materials as the expected Target product, thus providing an assessment of the safety (primary objective assessed in this study) and interfacing efficacy (secondary objective) of the technology.

² Trevathan JK, Baumgart I, Nicolai EN, et al. A Truly Injectable Neural Stimulation Electrode Made From an In-Body Curing Polymer/Metal Composite. BioRxiv. 2019 BioRxiv <https://doi.org/10.1101/584995>.

Preclinical animal and benchtop work has been successfully conducted to prove out the technology. The conduit placement is designed to be very similar to a lidocaine injection pain physicians provide as part of their daily practice today, utilizing fluoroscopic or ultrasound visualization during the procedure. Using a needle of 2 to 5 mm diameter as a trocar, a wire rope is inserted to be in close proximity to the nerve at one end of the conduit, while the other (“current collector”) end is left as a loop in the subcutaneous tissue. After closing the puncture wound with steri strips or sutures, the patient will be allowed to recover for a few days, allowing the injected conduit to stabilize. After a few days of recovery, electrical current to stimulate the nerve is applied on the outside of the skin with a TENS unit, from where it reaches the collector end just below the skin. Once the current reaches the collector end, it is transferred at a very low electrical impedance to the nerve target, providing the neuromodulation treatment.

The advantages of this solution are (1) that the signal generator is outside the body, eliminating the need for battery replacement surgeries and (2) that the puncture wound to place the conduit leaves a significantly smaller scar than current procedures to place neuromodulation electrodes, leads and signal generators.

This conduit represents an injectable electrode that is formed into its final shape inside the body, or Injectrode for short.

While Neuronoff, Inc. has tested all components of this system in preclinical benchtop and animal studies, including very successful long term biocompatibility studies of the actual Injectrode insert for up to 180 days, it was deemed to be in the best interest of study participants and the company to conduct the clinical work in **two subsequent clinical studies** that build on top of each other:

First a clinical study to document the safety and electrical interfacing efficacy of the Injectrode insert for up to 28 days. This early feasibility study focuses primarily on documenting biocompatibility by having the Injectrode insert placed just below the skin into the subcutaneous tissue. Based on extensive chronic work in animals a rejection reaction is not expected, but if it were to happen, would be very easily dealt with by explanting the small insert. After 28 days, a short electrical measurement would be used to confirm successful interfacing with the device just minutes prior to removal by a dermatologic surgeon. This study design allows for risk to be very minimal, enabling the NSR designation for this study. **The document in hand describes this first study.**

The second clinical study is designed to build on the knowledge of the successful first study and will evaluate the deployment of a longer version of the Injectrode insert from a subcutaneous location to a nerve at a depth of approximately one inch in depth measured from the skin. The second study thus represents an actual treatment efficacy study for a clinical condition. This second clinical study is a future study and **not** the one described in the document in hand.

